Project Name: The association between serum urea nitrogen to creatinine ratio and the survival in patients with DKD.

No.: v1.2 version Date: June 1, 2020

Study unit: Guangdong Provincial People's Hospital

Sponsor: Guangdong Provincial People's Hospital

Background

In 2013, the prevalence of adult diabetes in China was as high as 10.9%, with the number of patients exceeding 100 million. Diabetic kidney disease (DKD), as one of the main microvascular complications of diabetes, occurs in 20% ~ 40% of diabetes. Furthermore, Diabetes-related chronic kidney disease, the leading cause of chronic kidney disease, has become a serious public health problem and brought huge economic burden. How to realize the early prevention and treatment of DKD and improve its clinical outcomes raises our concerns.

Previous studies have shown that a low-protein diet (LPD) can retard renal function decline in patients with CKD mainly through the improvement of glomerular hyperfiltration/hyperfusion and tubule-interstitial damage, inflammation and fibrosis. The lower the baseline dietary protein intake (DPI), the slower the progression toward ESRD. Each 0.1 g/kg per day higher DPI at baseline was associated with a loss of kidney function that was faster by approximately 0.064 ml/min per year. In 2020, standards of medical care in diabetes of American diabetes Association (ADA) recommended for people with nondialysisdependent CKD to maintain DPI approximately 0.8 g/kg body weight per day. Previous studies provided some methods for dietary assessment such as 24-hour dietary recalls, food diaries and food frequency questionnaires, which exist limitations including:(1)reliance on patient's memory, compliance and communication ability; (2)reliance on interviewer's skills, comprehensiveness and prompts;(3)lack of ability to represent a longer period. Maroni formula, which tests 24-hour urine urea nitrogen, is a relatively objective and common method to evaluate protein intake, but can't be generalized due to its complexity and uncertainty. Joel D et.al found that serum urea nitrogen to creatinine ratio (sUCR) correlated closely with protein intake and knowledge of its relation to protein intake could be used to determine the degree of protein restriction. In our previous study, the mathematical model between sUCR and DPI was preliminarily established after modeling and verification, and has obtained the patent.

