Protein restriction is a basic but important life intervention to improve the prognosis of DKD patients. How to calculate DPI in a simple and effective way to overcome the complexities and errors of existing methods attracts our attentions. In this study, we hypothesize sUCR can be applied to evaluate of protein intake during the follow-up periods and predict the survival in patients with DKD.

Object

To evaluate the prognostic value of sUCR in the progression of DKD.

Methods

This study is a multicenter, retrospective cohort study. We select patients diagnosed with DKD since January 2012. The present study is performed according to the principles of the Declaration of Helsinki and has been approved by the Ethics Committee of Guangdong Provincial People's Hospital.

Study population

We screen DKD patients aged 18-70 years with CKD stages 1-4. DKD was defined as those diagnosed by pathological biopsy, or those with eGFR <60 ml/min per 1.73 m², or presence of clinically detectable albuminuria over 3 months which is caused by diabetes. Patients who undergo infection, severe liver disease, malignant tumor, acute heart failure, gastrointestinal hemorrhage, pregnancy are excluded.

Data collection

At baseline and every medical visit, therapeutic relevant information will be collected. Data mainly include demographic characteristics (age, gender, place of residence, marriage status, education degree), lifestyle (smoking, drinking, exercise), clinical characteristics (body mass index, blood pressure, duration, history of CVD, complications, nutrition situation), laboratory indexes (serum creatinine, blood urea nitrogen, glycosylated hemoglobin, urinary albumin to creatinine ratio, 24-hour urinary albumin, 24-hour urine urea nitrogen, etc.). History of cardiovascular disease including coronary artery disease, congestive heart failure, stroke, and peripheral vascular disease were ascertained by self-report or doctor's diagnosis.

Outcomes

Patients are followed for survival until they reach the end of the study, whichever happen first, or are censored because they lose contact or the follow-up interval is less than one month. The outcomes are all-cause death, a composite of end-stage kidney disease (dialysis, transplantation, or a sustained estimated GFR of <15 ml per minute per 1.73 m², or increasing by 50% of the serum creatinine level from baseline. Evaluated GFR was calculated using Chronic Kidney Disease Epidemiology Collaboration (CKD-EPI) formula.

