Statistics

Data are presented as mean \pm SD for continuous variables and as a number (percentage) for categorical variables. According to mean sUCR and Δ sUCR (fluctuation of sUCR over time, meaning monthly rate of change), patients are divided into four groups. The relationship between baseline characteristics among the four groups was compared by using one-way analysis of variance test, Kruskal-Wallis test or Chi-squared test where appropriate. Survival rates are estimated using Kaplan Meier analysis, and the significance of differences are analyzed using the log-rank test. Cox proportional hazard regression analysis is used to assess the association between the clinical outcomes and mean sUCR and Δ sUCR. In multivariate analysis, we enter variables using a P value of <0.10 as the selection criterion or considered clinically significant. Hazard ratios (HRs) are presented with 95% CIs. All statistical analysis was performed with the use of SPSS (version 19.0, SPSS, Chicago, USA) and Prism 7.0 (GraphPad Software, San Diego, CA, USA). A two-tailed P value <0.05 was considered to be statistically significant.

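### No primary outcome or exposure is named, and the title and hypothesis (survival) differ from the Object (progression), so the main result can be chosen after the data are seen

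*Combined protocol and SAP*

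**What the plan says.** The outcome of interest is described in four places.

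- Title: "The association between serum urea nitrogen to creatinine ratio and the survival in patients with DKD".
- Hypothesis, at the end of the Background: sUCR is expected to "predict the survival in patients with DKD".
- Object: "To evaluate the prognostic value of sUCR in the progression of DKD".
- Outcomes: "The outcomes are all-cause death, a composite of end-stage kidney disease (dialysis, transplantation", then a sustained low eGFR, then "or increasing by 50% of the serum creatinine level from baseline". In the text available, the bracket opened before dialysis is never closed.

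The Statistics section then states: "Cox proportional hazard regression analysis is used to assess the association between the clinical outcomes and mean sUCR and Δ sUCR". It also splits patients into four groups using the two sUCR measures, without cut-points, and compares survival curves by log-rank test. One threshold covers everything: "A two-tailed P value <0.05 was considered to be statistically significant".

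No section names a primary outcome, a primary exposure, an order of testing or an approach to multiplicity. Nothing in the text suggests that such a statement was blacked out.

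**The concern.** Death and kidney progression are different endpoints, and the average level of sUCR is a different exposure from its monthly rate of change. An association of mean sUCR with death and an association of ΔsUCR with a creatinine rise would be different scientific claims. The plan gives all such pairs equal standing, so either could be reported as the study's main finding.

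The design makes this more pressing. The cohort is retrospective, with patients diagnosed since January 2012, and the plan is dated June 2020. Some outcomes may already have been on record when it was written. In that setting a written primary analysis is one of the few safeguards against choosing the headline afterwards. Without one, a reader cannot interpret a single P<0.05 at its nominal 5%.

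**Working it through.** **No figure to reproduce.** The documents give no sample size, event count, power or familywise error rate.

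**Inputs from the documents**
- Threshold: 0.05, two-sided, per test (Statistics).
- Exposures: 2, mean sUCR and ΔsUCR (Statistics).
- Outcomes: 2 if the creatinine rise is part of the kidney composite, 3 if it stands alone (Outcomes; the open bracket leaves this unclear). A less natural reading puts death and all kidney events into 1 composite.

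**Assumed inputs (not in the documents)**
- Correlation between test statistics across outcomes: 0 to 0.8.
- Correlation across exposures: 0 to 0.5.

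**Step 1: count the Cox tests.** Tests k = exposures × outcomes, if each exposure is tested separately on each outcome:
- 2 × 1 = 2
- 2 × 2 = 4
- 2 × 3 = 6

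**Step 2: independent tests.** With no true association, P(at least one P<0.05) = 1 − 0.95^k:
- k = 2: 1 − 0.9025 = 0.0975
- k = 4: 1 − 0.8145 = 0.1855
- k = 6: 1 − 0.7351 = 0.2649

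Whatever the correlation, the value cannot exceed k × 0.05, which is 10%, 20% and 30%.

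**Step 3: correlated tests.** Multivariate normal statistics were simulated, 400,000 draws per setting, counting draws with any |z| above the two-sided 0.05 critical value. The correlation between two tests that differ in both outcome and exposure was the product of the two assumed correlations.

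| Correlation across outcomes | Correlation across exposures | 4 tests | 6 tests |
|---|---|---|---|
| 0 | 0 | 18.6% | 26.5% |
| 0.3 | 0.3 | 17.6% | 24.8% |
| 0.5 | 0.3 | 16.9% | 22.9% |
| 0.8 | 0.5 | 13.9% | 17.2% |

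The first row matches Step 2 within simulation error. For the single-composite reading (2 tests), an exposure correlation of 0.5 lowers 9.75% only to about 9.0%.

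**Step 4: what is left out.** The log-rank comparisons of the four groups and the choice between univariate and multivariate models are not counted. One log-rank test per outcome would bring the total to 6 to 9 tests. These overlap heavily with the Cox tests, so the independent formula would overstate their effect.

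**Step 5: after the change.** One named primary outcome and one named primary exposure give k = 1 and an error rate of 5% for that test.

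**The case against.** Several points on the other side have force.

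- **The threshold is per test.** A reader might infer that any single P<0.05 would make the study positive by its own rule. The documents do not say so: the sentence is a conventional per-test threshold and sets no success criterion. The gap is that nothing says which test carries the main claim.
- **This is an observational prognostic study.** It reports hazard ratios with 95% CIs, and formal multiplicity correction is debatable here. That stands. It does not remove the need to say which analysis is primary, because the Statistics section labels nothing exploratory.
- **The test count is not fixed.** The four groups may be a joint classification by both exposures, with one log-rank comparison per outcome, and the documents do not say how the exposures enter the Cox models. The missing bracket may also have been lost in text conversion. So four and six are conditional counts. Entering both exposures in one model would still give one P value per exposure per outcome, unless a joint test were used.
- **Survival may mean event-free survival.** Outcomes describes follow-up in terms of survival and then lists kidney events beside death, so the conflict may be loose wording. That is possible, but the plan does not define survival this way.
- **Naming a primary now may come too late.** If results have already been seen, the protection is only partial. This is a reason for disclosure, not for leaving the choice open.

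**Conclusion.** The concern holds: the plan does not rank its outcomes or exposures, and its statements of purpose do not agree on the outcome. If the two exposures are tested separately, the chance of at least one P<0.05 with no true association is about 14–19% for two outcomes and 17–27% for three. The lower ends assume strong correlation (0.8 across outcomes, 0.5 across exposures) and the upper ends assume none. Under the single-composite reading it is 9.75% for two independent tests. The correlations are assumptions, but every setting examined lies above 5%.

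A reader might also infer that the Object settles the matter in favour of the kidney composite with mean sUCR. The documents do not support that: the hypothesis sides with the title on survival, and the Statistics section gives both exposures equal standing. Nor do they show that results were looked at before the plan was written; the dates only make it possible.

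The planned analyses can still be run. What is affected is how far their significance claims can be taken.

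**What to change.** 1. Name one primary outcome and one primary exposure, tested at two-sided 0.05. The choice is the sponsor's: the kidney composite if the Object governs, all-cause death if the title and hypothesis govern.
2. Reword the title, hypothesis and Object so that all three match that choice.
3. Close the bracket in Outcomes and state whether the 50% creatinine rise is part of the composite or a separate outcome.
4. Label every other exposure–outcome pair secondary or exploratory, and report it as a hazard ratio with its 95% CI and without a confirmatory significance claim. Holm adjustment of these pairs is optional.
5. If any outcome data were examined before the primary analysis was named, say so.

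This takes a few sentences and no new data. The downside is that fewer results can be called statistically significant.
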